# Good clinical practices statement

This clinical study will be conducted in accordance with applicable Health Canada regulations, International Conference on Harmonization guidelines on current Good Clinical Practice, and the Declaration of Helsinki.

# Co-development process

Starting in April 2024, our research team has incorporated patients with lived experience of IgA nephropathy as co-investigators on this study. Through a series of monthly 1-hour meetings, each aspect of the protocol was discussed openly with our patient partners to obtain their feedback and address potential challenges particularly related to participant burden and safety. All patient-facing materials have been created and reviewed by the patient partners.

# **Abbreviations**

BP	Blood pressure
CI	Confidence interval
CRF	Case report form
DSMB	Data Safety and Monitoring Board
eGFR	Estimated glomerular filtration rate
GN	Glomerulonephritis
IgAN	Immunoglobulin A nephropathy
OHRI	Ottawa Hospital Research Institute
RAAS	Renin angiotensin aldosterone system
RCT	Randomized controlled trial
REB	Research ethics board
SGLT2	Sodium glucose transport protein 2
STOP-IgAN	Intensive Supportive Care Plus Immunosuppression in IgA Nephropathy
TASMIN-SR	Effect of Self-monitoring and Medication Self-titration on Systolic Blood
	Pressure in Hypertensive Patients at High Risk of Cardiovascular
	Disease
TESTING	Effect of Oral Methylprednisolone on Decline in Kidney Function or
	Kidney Failure in Patients With IgA Nephropathy

# Lay summary

Can self-management of blood pressure lead to better outcomes for patients with IgA nephropathy?

# Background

IgA nephropathy is a kidney condition in which an imbalance in the patient's immune system causes injury to the tiny filters within their kidneys leading to leakage of protein and blood into the urine, and decreased kidney function. Because IgA nephropathy tends to occur when patients are young, they have a high risk of developing kidney failure over their lifetime. Controlling blood pressure (BP) can protect their kidney filters from further injury. When done well, this treatment can help reduce the amount of protein in the urine (the best marker of kidney damage) and preserve kidney function. Despite the importance of BP control, there is no accepted standard for how BP should be measured and treated in patients with IgA nephropathy. By checking BP only at clinic visits, there are missed opportunities to detect and treat high BP appropriately.

# Purpose

This study aims to test whether patients with IgA nephropathy who self-manage their BP will have better BP control and less protein in their urine compared to patients whose BP is measured and treated only at kidney clinic visits.

### Methods

Self-management means that patients measure their BP at home and adjust the dose of their medications to a target BP value. A previous clinical trial conducted in patients without kidney disease showed that patients and their family doctors were able to successfully develop a self-management protocol. Working with our patient partners, we have adapted that protocol for patients with IgA nephropathy. The next step is to conduct a pilot clinical trial involving approximately 25 patients with IgA nephropathy who attend kidney clinics in Ottawa and Vancouver. Trial participants will be randomly chosen to either manage their BP using the self-management protocol or to be in the control group. Participants in the self-management group will be taught how to accurately measure their BP at home over a 7-day period each month. If most of these BP values are above target, they will contact the clinic for a new medication prescription

based on a 3-step plan which was developed with their doctor. Participants in the control group will have their BP measured and treated at clinic visits only. All participants will be followed for 6 months. At the end of the study period, we will measure BP and urine protein levels in all participants and compare these between the self-management and control groups. We will also interview participants in the self-management group to ask them about their experiences.

### Anticipated outcomes

The main outcome of the pilot trial is to find out if patients with IgA nephropathy will be willing to enter a trial of self-management of BP and to ensure that the protocol can be implemented safely and is not overly burdensome. The trial will also get preliminary information about whether self-management leads to better BP control and less protein in the urine.

# Patient engagement

Patients have been involved in every stage of this study from its design, including creation of patient-facing documents. The team of patient partners will continue to be involved through to completion of the pilot trial and sharing of the results.

# Relevance to patients and the kidney community

Patients living with IgA nephropathy have told us that their number one priority is preserving their kidney health and they would like to have more control over managing their condition. By developing an intervention with patients that can be implemented at home, this study seeks to meet both these needs. Protein in the urine is a strong risk factor for kidney failure and heart disease. If shown to be successful, a self-management approach could improve the long-term health of patients with IgA nephropathy and reduce healthcare costs.

### Conclusion

Good control of BP is critical to reduce the risk of kidney failure in patients with IgA nephropathy. What is learned from this pilot trial will be used to design a larger trial to answer the question of whether self-management of BP should be first choice in how to manage BP in patients with IgA nephropathy.

	
 
Proteinuria > 0.5 g/day quantified from 24-hour urine collection or urine protein:creatinine ratio >50 mg/mmol or urine albumin:creatinine ratio >30 mg/mmol
 
Clinic systolic BP >130 mmHg or diastolic BP >85 mmHg (automated office BP measurement)
 
Willing to self-manage BP
 

Exclusion criteria	Any of the following:
	Currently receiving immunosuppression or in need of urgent start immunosuppression (e.g., rapidly progressive glomerulonephritis or nephrotic syndrome)
	
 
Kidney failure defined by the need for dialysis, kidney transplantation or eGFR <15 mL/min
 

	Recent (within 3 months) history of acute myocardial infarction or stroke
	Heart failure with reduced ejection fraction
	Concomitant diabetic nephropathy on kidney biopsy
	Pregnancy (or actively planning a pregnancy) or breastfeeding
	Life expectancy <12 months
	Allergy or intolerance to both an angiotensin converting enzyme
	inhibitor and angiotensin II receptor blocker
	Severe hypertension (>180/100 mmHg)
Treatments	Intervention arm (study treatment)
	Self-management of BP including self-monitoring of home BP values and self-titration of medications according to a pre-specified individualized
	treatment plan
	Control arm
	Usual management of BP and anti-hypertensive therapy by a physician at regularly scheduled clinic visits
Sample size pilot trial	Target recruitment: 25 patients over 2 years across three sites (The Ottawa Hospital Glomerulonephritis Clinic and the Glomerulonephritis Clinic in Vancouver General Hospital and St. Paul's Hospital, Vancouver)
	Justification: The target sample size is primarily based on the incidence of
	IgA nephropathy and the anticipated recruitment rate from the clinic. We
	will seek to recruit newly diagnosed patients but will also include prevalent
	patients at each site. The target sample size should be sufficient to address
	practical questions regarding the feasibility of conducting a larger clinical
	trial with respect to recruitment, ease of implementation of the intervention,
	and collection of efficacy and safety outcomes. The total sample size of 25
	participants is further supported by a sample size calculation for the
	participanto is further supported by a sample size calculation for the

	feasibility metric of retention of participants in the trial. The progression criterion for this outcome is 80%. Assuming 90% of participants complete
	the 6-month study duration, a total of 26 participants would be needed to
	provide a one-sided 95% confidence interval of 10% (i.e. a lower bound
	estimate of 80%).
Expected	The pilot trial will ensure the feasibility of the full-scale trial for recruitment
outcomes from	of patients and adherence to the trial protocol. Participants in the self-
pilot trial	management arm will have a positive experience and will perceive the
	intervention as sustainable in the longer term.
Sample size	For a definitive trial, a sample size of 186 patients would provide 80%
estimation for full-	power to detect a mean between-group difference in systolic BP of 7
scale trial	mmHg (a more conservative effect size compared to previous studies)
	assuming a standard deviation of 17 mmHg.
Analysis for pilot	Feasibility will be defined as achieving target thresholds for both
trial	recruitment and retention. The protocol will be refined based on metrics of
	adherence to the intervention as detailed below:
	The probability of successful recruitment will be calculated as the
	percentage of eligible participants who are randomized. A threshold of
	>50% will be required for progression to a full-scale trial.
	2. The probability of retention will be calculated as the percentage of
	randomized patients who complete the study. A threshold of >80% will be
	sought for progression to a full-scale trial.
	3. Adherence to the self-management protocol will be quantified for each
	participant using the median number of recorded home BP readings per
	measurement week and further explored in participant diaries and
	interviews. There is no threshold for progression to a full-scale trial;
	however, the protocol will be refined based on these factors.
Analysis for full-	The between-group difference in mean systolic BP will be the primary
scale trial	outcome in a future full-scale trial. This will be evaluated using mixed
	models adjusting for baseline BP, sex, and site (as a random effect). The
	proportional change in proteinuria across study visits will be analyzed using
	a ratio of geometric least squared means.
Study visits	Study visits will occur in-person at baseline (time of randomisation), then at
	week 12 and a final study visit at 26 weeks. Participants in the self-
	management group will have one additional visit at or close to the time of
	randomization for teaching and training.

# 1. Background and rationale

1.1 Reducing proteinuria is an important goal in IgA nephropathy Immunoglobulin A nephropathy (IgAN) is a type of glomerulonephritis, a group of autoimmune diseases that cause inflammation of the filtration units of the kidney and lead to leakage of protein and blood into the urine (proteinuria and hematuria). Patients with IgAN are typically diagnosed at a relatively young age compared to those with other forms of chronic kidney disease, and as such they have a high lifetime risk of kidney failure. 1 Observational studies and meta-analyses of clinical trials have consistently demonstrated that reducing proteinuria is associated with lower risk of disease progression and kidney failure in patients with IgAN. and a reduction in proteinuria is now accepted as a surrogate endpoint in clinical trials. Our previous work with the International IgA Nephropathy Network showed that each 3 months in proteinuria remission was associated with an additional 9% reduction in the risk of kidney failure. 6 Achieving a sustained reduction in proteinuria is therefore an important outcome for patients because it can reduce the risk of needing dialysis or a kidney transplant in the future, translating to fewer complications for patients and lower costs to the health care system.

### 1.2 How can a reduction in proteinuria be achieved?

Although immunosuppression treatment is available for patients with IgAN, it comes with a risk of serious infections and is therefore typically reserved for high-risk patients (defined as the presence of persistent high-grade proteinuria, usually ≥1 g/day). Consideration for immunosuppressive treatment is determined after an observational period of approximately 6 months following diagnosis via kidney biopsy, during which time patients receive non-immune or "supportive" therapy. The cornerstone of supportive therapy in IgAN is blood pressure (BP) control through the use of renin angiotensin aldosterone system (RAAS) inhibitors which have been shown to reduce proteinuria and improve kidney outcomes in non-diabetic patients with proteinuria, 10 including patients with IgAN. 11,12 In prospective studies, with BP management alone, up to 50% of patients with IgAN can achieve partial or complete remission of their disease based on a reduction in proteinuria. Since IgAN is a chronic disease, supportive care

needs to be maintained throughout the patient's illness trajectory, irrespective of the decision to pursue short courses of immunosuppression.

# 1.3 How should supportive care be delivered?

Despite the recognized benefits of supportive therapy, there is no uniform strategy that defines optimal supportive care. This can be readily seen from two recent randomized controlled trials (RCTs) of immunosuppression for IgAN, which entered participants who met inclusion criteria in a run-in phase with the intent of maximizing supportive care prior to randomization. The STOP-IgAN trial (N=309) followed patients monthly for 6 months and titrated the dose of RAAS inhibitor to target BP <125/75 mmHg at each visit, along with offering lipid-lowering therapy and counseling about a low-sodium diet and smoking cessation, while the TESTING trial (N=523) had a run-in phase of 4 to 12 weeks (for a total of two to three study visits) to ensure that all participants were on a RAAS inhibitor for 3 months prior to randomization but had no BP target. Despite the different approaches used, 34% (n=106) of patients who completed the run-in period in STOP-IgAN achieved a response (reduction in proteinuria to <0.75 g/day), and 24.5% (n=128) of patients in TESTING experienced a reduction in proteinuria to the extent that they no longer met the inclusion criteria for randomization.8 These two RCTs show that a substantial proportion of patients can achieve at least a short-term reduction in proteinuria with supportive therapy alone. However, there remain some important knowledge and care gaps. It is unclear whether the need for frequent in-person visits, beyond what is typical in routine care, would be feasible in most settings, as well as potentially placing additional burden on patients. Trial participants have not been randomized during the run-in phase of contemporary RCTs and no specific supportive care interventions have been formally tested, including the systolic BP target of 120 mmHg suggested by international guidelines.

The current standard of care for BP treatment is according to automated office BP readings at in-person clinic visits. Among 91 patients with incident IgAN diagnosed on a kidney biopsy between January 2020 and December 2022 at The Ottawa Hospital, 58% of patients had a systolic BP >120 mmHg and 38% of patients were receiving sub-

maximal doses of a RAAS inhibitor at six months' follow-up ([name], personal communication). Studies of ambulatory BP monitoring in patients with glomerulonephritis have shown a high prevalence of masked hypertension, nocturnal hypertension, and non-dipping status, 15,16 highlighting the limitations of relying solely on clinic BP readings. In one cross-sectional study, systolic BP from ambulatory monitoring had a stronger correlation with both kidney function and albuminuria compared to systolic BP from clinic readings. In a small prospective study, patients with glomerulonephritis who had normal clinic BP and preserved kidney function were found to have higher ambulatory BP values compared to matched controls, along with early evidence of left ventricular hypertrophy. Targeting ambulatory BP has not been systematically evaluated in patients with IgAN and could provide opportunities for earlier intensification of RAAS inhibitor therapy, better overall BP control and improvements in proteinuria.

# 1.4 Could patients manage their own blood pressure?

Self-management is well established for chronic health conditions such as diabetes mellitus (glucose monitoring and insulin titration), heart failure (weight monitoring and diuretic adjustment), and asthma (peak flow monitoring for earlier detection of exacerbations). Self-management can in turn promote self-efficacy, with downstream health benefits for patients living with a chronic disease. A report from the Standardizing Outcomes in Nephrology-Glomerular Disease initiative found that patients with glomerular disease prioritized preservation of their kidney function above all else, and reported impaired agency or loss of control over their health. Furthermore, an international focus group study of self-management in glomerular disease involving 135 patients and their care partners found that a key facilitator to self-management was "Empowered in Autonomy" whereas an important barrier was frustration arising from fragmented and inflexible care models. Patients sought greater responsibility for treatment decision-making, home monitoring, and making positive lifestyle changes. A key recommendation from this work was to utilize existing self-management interventions that have been shown to be effective in other conditions to inform

strategies for use in glomerular disease, as well as co-designing and co-implementing these interventions with patients.

A series of RCTs in the primary care setting have evaluated the efficacy and safety of self-monitoring of home BP values and self-titration of anti-hypertensive therapy.  Of particular interest to us is the Effect of Self-monitoring and Medication Self-titration on Systolic Blood Pressure in Hypertensive Patients at High Risk of Cardiovascular Disease (TASMIN-SR) trial, which demonstrated that self-management of BP was superior to usual care after 12 months of follow-up with mean reduction in systolic BP of 9.2 mmHg (95% CI 5.7 to 12.7) in individuals with hypertension at high-risk for cardiovascular events.  The majority of participants in the self-management group measured their BP properly and recorded the values accurately.  No significant differences in adverse events were noted compared to usual care.

# 1.5 Why is a trial needed?

There are important differences between the population studied in TASMIN-SR and patients with IgAN. First, it is recommended that patients with IgAN receive maximally tolerated doses of a RAAS inhibitor as first-line therapy. Second, many of these patients have reduced kidney function at the time of diagnosis, and the efficacy and safety of self-management has not been studied in this context. Third, supportive care should be optimized within a shorter time-frame than that studied in TASMIN-SR (6 months versus 12 months) and the feasibility of self-management to achieve this has not been demonstrated. To improve the likelihood of achieving proteinuria reduction, there is a need to standardize the approach to supportive care in IgAN with a treatment strategy that is co-developed with patients to ensure appropriateness and acceptability, can be delivered outside of clinic visits, is readily implementable in clinical care, and can be upscaled for use in the run-in phase of clinical trials.

#### 1.6 Benefits and risks

Self-management could have many benefits for patients. First, it could facilitate earlier control of BP by helping patients achieve their target BP more efficiently. This, in turn,

could lead to earlier reduction in proteinuria, which has been identified as a surrogate outcome for future kidney health. Second, self-management provides a way for patients to take more ownership over their kidney health. The need for patient autonomy in aspects such as home monitoring and lifestyle measures was identified in focus groups as a key priority for patients and caregivers. Third, if patients feel that self-management strategies are sustainable this approach could have the potential to improve the long-term kidney and cardiovascular health of patients with IgAN through better monitoring of BP and earlier identification of suboptimal BP control.

Prior studies have demonstrated that self-management of BP and self-titration of medications can be achieved safely, including in individuals with complex medical problems such as a prior stroke. We recognize that participants may feel apprehensive or overwhelmed about having to self-manage their blood pressure. The potential for participant burden has been a major focus for our team in development of this protocol. Our patient partners have provided feedback about each step of the process to mitigate this risk. Other potential risks are described in section 9.1.

# 2. Study objectives and research questions

# 2.1 Primary objective of SMART-IgAN pilot

To determine the feasibility of a full-scale trial by showing that self-management of blood pressure is acceptable to patients and achievable in the clinic setting.

Hypothesis: At least 50% of eligible patients will be randomized; at least 80% of participants will complete the study.

# 2.2 Secondary objective of SMART-IgAN pilot

To evaluate patient experience of self-management through a monthly diary entry and a semi-structured interview at the end of the study.

Hypothesis: Participants who self-manage their BP will view the intervention as a positive experience and will perceive the intervention as sustainable in the longer term.

### 2.3 Primary objective of SMART-IgAN full-scale trial

Compare the achieved BP in patients randomized to self-management versus patients receiving usual care in the clinic.

Hypothesis: Patients who self-manage their BP will have lower BP at the end of the study period compared to patients whose BP is managed in the clinic.

# 2.4 Secondary objective of SMART-IgAN full-scale trial

Evaluate the effect of self-management on proteinuria reduction.

Hypothesis: Patients who self-manage their BP will experience a greater reduction in proteinuria compared to patients whose BP is managed in the clinic.

# 3. Outcomes

# 3.1 Primary outcome

The primary outcome of the pilot trial will be feasibility defined as achieving target threshold for both recruitment and study completion. The study protocol will be revised based on adherence metrics and participant feedback as detailed below:

- 1. The probability of successful recruitment will be calculated as the percentage of eligible participants who are randomized. A threshold of >50% will be required for progression to a full-scale trial.
- 2. The probability of retention will be calculated as the percentage of randomized patients who complete the study. A threshold of >80% will be sought for progression to a full-scale trial.
- 3. Adherence to the self-management protocol will be quantified for each patient in the intervention group using the median number of recorded home BP readings per measurement week. Adherence will be further explored from participant feedback in longitudinal diary entries and a semi-structured interview. Fidelity of the intervention will also be explored retrospectively by comparing the submitted BP readings to the BP readings downloaded from the machine at the end of the study period. There is no progression criterion for adherence but the study protocol for a future full-scale trial will be refined based on these factors.

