# 5. Study population

The target population for SMART-IgAN includes adult patients with a diagnosis of IgA nephropathy confirmed on a kidney biopsy and suboptimal BP control. Potential participants at The Ottawa Hospital will be identified using (i) an existing registry of patients who have biopsy-confirmed IgA nephropathy (the Ottawa GN database) and/or (ii) a clinic planner (a Word document that is completed by a physician prior to the clinic that lists the patients attending the clinic on a specific day and includes information about their underlying diagnosis and a summary of their care plan). The Ottawa GN database is housed within the Ottawa Hospital Research Institute (OHRI) and is

password protected. The clinic planners are housed in a folder on SharePoint and are only accessible to physicians, nurses and administrative staff who work in the GN clinic.

Clinic patients who are potentially eligible for recruitment will be contacted by phone outside of their regularly scheduled clinic visit by either a healthcare professional within their circle of care or by a research coordinator. Patients who indicate a willingness to participate in the study will be offered the opportunity to read the consent form prior to their in-person clinic visit, at which time full eligibility will be determined based on their BP value in the clinic. Patients who meet all inclusion criteria will be consented and randomized on the same day as their scheduled clinic visit. If this is not feasible (for example due to time constraints), they will be offered an alternative date to return to the clinic for completion of the consent form.

Individuals who decline to participate will be asked if the following information may be collected so that the investigators can compare individuals who complete the study to those that elect not to participate: (i) reason(s) for not wishing to participate; (ii) demographic characteristics (sex, decade of age); (iii) clinical characteristics (level of kidney function, degree of proteinuria, clinic blood pressure value).

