### 5.1 Inclusion criteria

- Adult patients aged ≥18 years who provide written informed consent.
- Biopsy-confirmed diagnosis of IgAN.
- Proteinuria > 0.5 g/day quantified from 24-hour urine collection or urine protein:creatinine ratio >50 mg/mmol or urine albumin:creatinine ratio >30 mg/mmol.
- Clinic systolic BP >130 mmHg or diastolic BP >85 mmHg (automated office BP measurement)
- Willing to self-manage BP

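### The recruitment progression criterion divides by eligible patients, but the protocol gives eligibility two incompatible meanings and leaves phone decliners uncounted

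*Protocol*

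**What the plan says.** Protocol section 3.1, repeated in the synopsis, defines the recruitment criterion: "The probability of successful recruitment will be calculated as the percentage of eligible participants who are randomized". It adds: "A threshold of >50% will be required for progression to a full-scale trial". Retention is the only other progression criterion; adherence has no threshold. The hypothesis in section 2.1 words the threshold differently: "At least 50% of eligible patients will be randomized". The aim stated there is to establish feasibility by "showing that self-management of blood pressure is acceptable to patients and achievable in the clinic setting".

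The formal eligibility list in section 5.1, also in the synopsis, includes "Adult patients aged ≥18 years who provide written informed consent" and "Willing to self-manage BP".

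Section 5 has potential participants phoned outside their clinic appointment. Those who express interest may read the consent form before the visit, "at which time full eligibility will be determined based on their BP value in the clinic". People who decline are asked whether their reasons, demographics, kidney function, proteinuria and clinic BP may be recorded. The section does not say whether they enter the recruitment percentage.

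Two other places use the word differently. Section 8 describes eligible patients, some of whom are willing and go on to consent and randomization. Section 12.1 expects 30 of 60 newly diagnosed Ottawa patients to be eligible and aims to recruit half of those, 15.

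**The concern.** The denominator decides what this criterion measures. If eligibility includes consent and willingness, refusers are removed by definition, and the ratio shows only whether people who have already agreed go on to be randomized. Refusal is the most direct recruitment evidence that self-management is not acceptable, and it would not appear in the figure.

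If eligibility is settled before consent, the ratio does measure uptake. But someone who declines on the phone has not reached the visit at which BP completes the eligibility check, so may never be classed as eligible.

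Two teams could therefore take the same screening log and report very different percentages for a go/no-go criterion, both citing the protocol. If decliners are not logged in a way that allows classification, the gap cannot be fully repaired afterwards.

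**Working it through.** **The plan's own figure.** From section 12.1, 2 years × 30 diagnoses = 60; half eligible gives 30; half of those recruited gives 15; adding 10 from Vancouver gives 25. This reproduces the stated target. It makes sense only if 15 people who are not recruited stay in the denominator, which is a denominator set before consent.

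**Literal 5.1 denominator (willing and consented).** The metric is P(randomized | willing and consented) and does not depend on uptake. Suppose 20% of 30 clinically eligible patients accept and 90% to 100% of those are randomized (both assumed).
- Randomized: 30 × 0.20 × 0.90 = 5.4, up to 30 × 0.20 × 1.00 = 6.
- Uptake: 18% to 20%.
- Reported metric: 90% to 100%.

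Exact binomial chance of exceeding 50%:

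| Denominator | Needed to pass | 80% randomized | 90% randomized |
|---|---|---|---|
| 15 | at least 8 | 0.9958 | 0.99997 |
| 25 | at least 13 | 0.9996 | >0.999999 |

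**Denominator before consent.** Take the Ottawa planning figure of 30, so passing needs at least 16. The uptake rates are assumptions.

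| True uptake | Chance of passing |
|---|---|
| 20% | 0.00005 |
| 30% | 0.006 |
| 40% | 0.097 |
| 50% | 0.43 |
| 60% | 0.82 |

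Here the criterion discriminates.

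**Phone decliners under the second definition.** Let 12 of 30 clinically eligible patients be randomized (40%, a fail). If d of the 18 decliners refuse by phone and are never classed as eligible, the reported figure is 12/(30 − d). With d = 6 it is 12/24 = 50.0%, still a fail; with d = 7 it is 12/23 = 52.2%, a pass. The counts 12 and d are assumed, to show how few uncounted refusals can change the decision.

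**Threshold wording.** The planned 15 of 30 is exactly 50%. It meets the hypothesis in 2.1 and fails the criterion in 3.1. At 50% true uptake the chance of at least 16 of 30 is 0.428; by symmetry the chance of at least 15 is 1 − 0.428 = 0.572.

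**The case against.** The strongest reply is that the literal reading is not the intended one. Section 8 places willingness and consent after eligibility. Section 5 has patients meeting the inclusion criteria and then being consented, although consent is itself on that list. Section 12.1 works the metric through with 30 in the denominator and 15 recruited, and the hypothesis in 2.1 would be empty if refusers were excluded. This stands. A reader might infer that the criterion can hardly fail, or that the trial would be called feasible almost regardless of uptake. The documents do not support that as a description of the plan; it follows only from applying 5.1 to the letter.

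Second, refusals are not ignored. Section 8 allows patients to be approached at the clinic visit, where BP is measured the same day, and section 5 seeks reasons and clinical data from decliners. This stands in part: the data would help to classify decliners, but collection depends on their agreement, and nothing says they are counted.

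Third, acceptability is also addressed by retention, adherence, diaries and interviews. True, but all of these come from randomized participants, and the diaries and interviews from the self-management arm only. None captures people who said no.

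Fourth, an analysis plan not seen here might define the denominator. It could, but the conflict lies between sections of the protocol itself.

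A reader might also infer that the criterion is defective because it ignores the rate of accrual. The protocol states a target ("Target recruitment: 25 patients over 2 years across three sites"), and using a proportion rather than a rate for progression is a design choice. Projecting the pilot's pace onto the full-scale trial would assume that no sites are added, which the protocol does not say.

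**Conclusion.** The point holds as an inconsistency in a primary progression criterion. Section 3.1 divides by eligible patients; section 5.1 puts consent and willingness inside eligibility, while sections 8 and 12.1 put them after it. Which sense is applied moves the chance of passing from above 0.99 to between 0.00005 and 0.097 when true uptake is 20% to 40%. This assumes 80% or more of consenting patients are randomized, denominators of 15 or 25 on the literal definition, and the Ottawa planning figure of 30 on the other.

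The definition set before consent is probably the one meant, and with it the threshold is a real test. A smaller defect remains there: phone decliners who would have met the BP criterion drop out, which biases the percentage upward. The size of that bias cannot be computed from the protocol, because it gives no number for phone refusals.

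**What to change.** In section 3.1 and the synopsis, define the recruitment denominator as all screened or approached patients who meet the clinical inclusion criteria (age, biopsy, proteinuria, clinic BP) and no exclusion criterion. State that the consent and willingness items of 5.1 are conditions for enrolment only and do not affect this denominator.

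Count decliners at every stage, including by phone. Automated clinic BP is already routine in these clinics, so it will often exist for a decliner, but section 5 makes recording it conditional on agreement. Report the percentage both with and without decliners whose BP is unavailable or may not be collected, and name in advance which of the two is compared with the threshold. Bring the use of *eligible* in sections 5, 5.1, 8 and 12.1 into line.

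Choose either at least 50% or more than 50%, and use it in 2.1, 3.1 and the synopsis.

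The cost is a few sentences, slightly more screening-log work, and a recruitment percentage that will probably look somewhat less favourable. Sample size, visits and enrolment rules do not change.
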